9. STUDY DRUG MATERIALS AND MANAGEMENT

9.1. Study Drug Packaging, and Labeling and Storage

Study drug supplies will be packaged identically so as to maintain the integrity of the study blind. The study medication bottles will be labeled minimally with the following information: study number TNX-CY-P301, sponsor name and address, bottle number, quantity, storage

conditions, usage instructions, and caution statements for investigational new drug, i.e., Caution: New Drug Limited by United States Law to Investigational Use, and Keep Out of Reach of Children and Pets.

Each study medication bottle will contain 40 tablets. Two bottles will be dispensed to each patient at Visit 2 (baseline), Visit 4 (Week 4) and Visit 5 (Week 8); this will provide the patient with 80 tablets to cover the 4 weeks of dosing between visits, plus additional tablets to cover loss and/or visit window variability. The patient should be instructed to take all the tablets in one bottle before opening the second bottle. The patient should be instructed to keep this study medication in a safe location out of extreme environmental conditions and out of the reach of children and pets, and be instructed that this medication is not to be taken by any individual other than the study patient. Each patient will also be instructed that they will be expected to return both bottles and all unused study medication at each clinic visit; unused medication will be counted to assess compliance with study drug treatment.

Storage of the study drug at the investigational site should be under locked and secure conditions with limited staff access. Study drug should be stored at 20-25°C/68-77°F in a temperature/humidity-monitored room; however, brief excursions (15-30°C/59-86°F) as defined in the Study Reference Manual (IP Receipt and Storage) are permitted without the sponsor's approval.

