9.2. Dosing Instructions

Patients will be instructed to take **two** tablets of their assigned study drug (TNX-102 SL 2.8 mg tablets or placebo tablets) sublingually, placed simultaneously **under the tongue**, each evening at bedtime starting at bedtime on evening of Day 0 (Day of Visit 2) and continuing without interruption for 12 weeks. The study drug should be taken at bedtime after teeth brushing and other oral care has been completed. The mouth/sublingual area should be moist at the time of dosing, so the patient should drink a few sips of water prior to dosing, especially if prone to dry mouth. Patients will be instructed to place the two SL tablets under their tongue and keep them there until they have dissolved. They should not swallow, crush or chew the tablets. Patients should not eat or drink (or chew gum) for at least 15 minutes after dosing, and preferably not until morning. Patients will be reminded that only 2 (two) tablets are allowed per day. Note: In the event that the patient misses a dose, instruct the patient to continue dosing with two (2) tablets the next evening; i.e., they should not take more to make up for the missed dose.

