9.5. Study Drug Accountability and Reconciliation

All patients will be expected to bring their bottles of study medication with them to all study visits. At each study visit, the site staff will inspect the medication bottles, and perform a count of the tablets remaining in the bottles and document this in the patient’s record. An assessment of medication adherence should be done by the study staff to ensure that the patient understands all dosing instructions and is taking the medication as prescribed. Patients will be asked for an explanation if the count of returned study drug tablets indicates a discrepancy between the expected number of tablets dosed and the number returned in the bottles. If it is found that the patient is not taking the study medication as expected, the patient will be re-counseled with instructions, and this should be noted in the patients’ records. A deviation should be recorded on any patient who is less than 70% compliant with dosing between visits.

If the patient fails to return any of the unused study drug as expected, the patient should be questioned regarding the reason for the lower than expected tablet number and about potential misuse, abuse or diversion. If more than 8 tablets cannot be accounted for at any of the visits where drug is returned (week 4, 8 or 12), the investigator will be asked to evaluate the situation, and a written summary of this evaluation should be added to the source and entered onto the case report form (CRF). Situations where replacement drug is requested, or when more than 8 tablets cannot be accounted for, should be recorded as deviations.

All study medication, including partial and empty bottles, must be maintained at the study site until Tonix or its designee verifies drug accountability and provides instruction for destruction or the return of the investigational product to the Sponsor’s drug distribution depot.

Tonix or their designee will perform drug accountability which entails reconciliation between the amount of drug shipped to the study site, study drug assigned and dispensed to the patient (including returned unused assigned study drug), and study supplies that were never dispensed and/or assigned to patients.

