### 11.2 Exposure and Compliance

The treatment duration will be calculated as (number of days=last dose date - first dose date+1) and summarized. Participants that are lost to follow up or have a missing last dose date will be assigned a last dose date of the day before the last attended clinic visit for analysis purposes.

All pill count shortage (negative pill count) of greater than 4 doses (8 tablets) per 4-week assessment period and/or any between-visit compliance <70% will be considered protocol deviations, and the reason for the pill count discrepancy will be discussed with the participant and documented in the CRF to ensure that any cases of potential abuse or misuse are identified. Participants with more than one significant incidence of negative pill count discrepancy during the double-blind phase of the study will be closely monitored by the investigator.

Exposure will be measured using the last date of treatment and first date of treatment. Total exposure will be defined as the last date of treatment minus the first date of treatment plus one. The number of participants with total exposure by visit weeks ( $\leq 4$  weeks (study day 0 to 28), 4 to  $\leq 8$  (study day 29 to 56), 8 to  $\leq 12$  (study day 57 to 84) and  $> 12$  weeks (study day  $\geq 85$ )) will be presented. Additionally, exposure days, defined as the total number of tablets taken divided by 2 (and rounded up to the nearest whole number), will be summarized.

Compliance will similarly be summarized across all study visits for each treatment arm. Study drug compliance as a percentage will be defined as the number of pills taken by the participant divided by the total number of pills that the participant was assigned to take multiplied by 100.

For calculating the compliance and exposure days, the following convention will be applied: for periods where drug is issued, but the participant does not return any bottles or tablets, or the participant misses the visit entirely, that period will not contribute to the compliance or exposure calculation unless the bottles are returned at a later visit.

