Compliance will be summarized with descriptive statistics by treatment arm. The number and percentages of participants within certain categories of compliance e.g. < 50%, 50% to < 70%, 70% to <= 100%, greater than 100% will be presented. Compliance between 70% to 114% will not be considered a protocol deviation. Tablet counts, calculation of compliance overall and by visit, and participant-reported reasons for all tablet discrepancies at all visits will be presented in a listing.

In addition, participants with significant over-usage or otherwise unaccounted-for missing tablets resulting in >114% compliance for any visit (e.g., failure to return >8 tablets per 4 week interval) will be summarized by visit and overall. These listings will include both the participant-reported reason for the discrepancy plus the investigator's assessment of potential abuse, misuse or diversion. Tables will be created for higher level abuse-related MedDRA terms. Clinically significant drug accountability discrepancies associated with missing medication, loss of drug, or cases in which the PI confirms concern over drug abuse, misuse or diversion, will be examined and discussed in the CSR.

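### SAP 11.2: a period with no drug return has no compliance value, so it cannot trigger the over-use and unaccounted-for-tablet summary, which is selected by compliance above 114%

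*SAP*

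**What the plan says.** SAP 11.2 gives this definition of compliance: "the number of pills taken by the participant divided by the total number of pills that the participant was assigned to take multiplied by 100". It then sets a convention for calculating compliance and exposure days in periods for which drug was issued: "the participant does not return any bottles or tablets, or the participant misses the visit entirely, that period will not contribute to the compliance". The sentence closes with an exception: "or exposure calculation unless the bottles are returned at a later visit".

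Further on, the same section specifies a summary of "participants with significant over-usage or otherwise unaccounted-for missing tablets resulting in >114% compliance for any visit". The example and the form of presentation follow: "e.g., failure to return >8 tablets per 4 week interval) will be summarized by visit and overall". The next sentence says that these listings carry both the participant's explanation and the investigator's judgement on abuse, misuse or diversion.

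The protocol supplies the quantities and the site procedure:

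- **9.1:** two bottles of 40 are dispensed at Visits 2, 4 and 5; "this will provide the patient with 80 tablets to cover the 4 weeks of dosing between visits", plus spares for loss and visit windows.
- **9.2:** "Patients will be reminded that only 2 (two) tablets are allowed per day".
- **9.5:** when unused drug does not come back, "the patient should be questioned regarding the reason for the lower than expected tablet number and about potential misuse, abuse or diversion". Where the unexplained shortfall at a return visit exceeds 8 tablets, the investigator's evaluation goes into source and CRF, and the event is a deviation.

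**The concern.** The summary is selected by a number that the convention takes away. A period without a compliance value cannot exceed 114%, so non-return is the one pattern of missing tablets that cannot trigger the rule. The example given with the rule nevertheless describes non-return. A programmer who follows the percentage leaves these periods out, and one who follows the example puts them in. The SAP does not say which governs.

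At stake is the only tabulation of unaccounted-for tablets by visit in the SAP, together with the listing specified to show the investigator's assessment of abuse, misuse or diversion. On the literal rule both would undercount.

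**Working it through.** **Inputs.** Dispensed per period: 2 × 40 = 80 tablets (Protocol 9.1). Scheduled: 2 per day (Protocol 9.2), so 2 × 28 = 56 over a nominal 4-week interval. Compliance = 100 × taken / assigned (SAP 11.2).

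**Reproducing the 114% cut-off.** (56 + 8)/56 = 64/56 = 114.29%. The threshold is therefore the 8-tablet limit written as a percentage. There is a small mismatch at the boundary: exactly 8 excess tablets gives 114.29%, which is above 114% but is not more than 8 tablets.

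**Applying the rule to one 28-day period.** Tablets not returned are treated as taken.

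| Returned | Compliance | Excess over schedule | Flagged by >114%? |
|---|---|---|---|
| 24 tablets | 56/56 = 100% | 0 | No |
| 17 tablets | 63/56 = 112.5% | 7 | No |
| 15 tablets | 65/56 = 116.1% | 9 | Yes |
| Two empty bottles | 80/56 = 142.9% | 24 | Yes |
| Nothing at all | No value (80/56 = 142.9% if counted) | 24 | No |

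The last two rows have the same arithmetic excess and opposite outcomes. In the last row none of the 80 tablets has been verified.

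**Overall figure.** Take one unreturned period and two perfect ones. Under the convention, overall compliance is (56 + 56)/(56 + 56) = 100%. With the 80 tablets counted as taken, it is (80 + 112)/168 = 114.3%. The first figure is defensible as an average-compliance statistic, but it cannot serve as a search for missing drug.

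**Dependence on interval length.** Excess on full non-return = 80 − 2 × days. The visit windows in Protocol 10.4 and 10.5 give:

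- Visit 2 to 4: 23–33 days, excess 34 down to 14.
- Visit 4 to 5: 18–38 days, excess 44 down to 4.
- Visit 5 to 6: 18–40 days, excess 44 down to 0.

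At 35 days the excess is 10 (80/70 = 114.3%). At 36 days it is 8 (80/72 = 111.1%), which is no longer more than 8. A full non-return over a long interval therefore need not breach the limit on either measure.

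**The case against.** The strongest reply is that this is a drafting ambiguity with little consequence, because the cases are reported elsewhere. A shortage of more than 8 tablets is a deviation by tablet count, independent of the 114% figure (SAP 11.2, Protocol 9.5). Deviations are summarized by type and arm (SAP 8.2). Tablet counts and participants' reasons for all discrepancies at all visits are listed with no threshold. The CSR discussion of clinically significant missing medication is not tied to 114% either. The convention itself opens by limiting its purpose to compliance and exposure days.

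Most of that stands, and it rules out several stronger readings that a reader might infer:

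- **That every non-return period is lost for good, or that such participants can never appear.** Bottles returned later bring the period back, and the any-visit wording lets another period bring the participant in.
- **That the largest shortfalls are the ones removed.** Empty-bottle returners have the same 24-tablet excess and are flagged. Non-return periods are unverified; the documents do not show them to be larger.
- **That the cases vanish from reporting, or that the CSR would reach a wrong conclusion on abuse potential.** The routes above reach many of them.

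These routes are not full substitutes. The deviation summary is not specified by visit and covers the Safety population, and SAP 6 excludes from that population anyone with no follow-up showing that drug was taken. For the general tablet listing, SAP 11.2 specifies participants' reasons but not the investigator's assessment. Limiting the convention to compliance does not help when the selection rule is itself a compliance value.

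**Conclusion.** The rule is wrong as written, with minor severity. Read literally, a non-return period cannot place a participant in the over-use and unaccounted-for-tablet summary, and this contradicts the example in the same sentence. For a nominal 28-day interval the missed excess is 24 tablets, three times the 8-tablet limit (24/8).

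This rests on two assumptions: that the percentage governs over the example, and that compliance means the same thing in both rules. SAP 11.2 defines only one such measure. The 24-tablet figure also assumes a 28-day interval.

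The documents give no basis for estimating how many participants would be affected, so the undercount is unquantified. Efficacy, compliance and exposure results are unaffected, and the convention is reasonable for the last two.

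**What to change.** In SAP 11.2:

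1. State that the non-return convention applies only to the compliance and exposure-day statistics, and not to selection for the over-use and unaccounted-for-tablet summary or its listing.
2. Define that summary on tablets: dispensed minus returned minus scheduled for the actual interval, flagged when more than 8. Include attended visits at which nothing was returned. This also removes the mismatch at exactly 8 tablets.
3. Add a row, by arm and visit, for drug dispensed with nothing returned where the visit was missed or the participant was lost. Base it on all participants issued drug, so that the Safety population exclusion does not remove them.

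Because the excess depends on interval length, the count will not flag every non-return: at 36 days it is exactly 8.

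The cost is a few sentences and one table row. Site staff already record the counts under Protocol 9.5, and no procedure changes. The downside is a somewhat higher reported number of participants with unaccounted-for drug.

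### SAP 11.2 counts a period with no returned bottles as zero in exposure days, so a fully dosed completer can be summarised with 56 days beside about 84 days by dates and 100% compliance

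*SAP*

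**What the plan says.** SAP 11.2 gives three descriptions of how much drug a participant received.

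- **Dates.** "Total exposure will be defined as the last date of treatment minus the first date of treatment plus one". Treatment duration and the exposure categories by visit week also rest on dates.
- **Exposure days.** "exposure days, defined as the total number of tablets taken divided by 2 (and rounded up to the nearest whole number), will be summarized".
- **Compliance.** The "number of pills taken by the participant divided by the total number of pills that the participant was assigned to take", as a percentage.

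One convention then covers the two tablet-based measures: "For calculating the compliance and exposure days, the following convention will be applied". It is triggered when drug was issued but "the participant does not return any bottles or tablets, or the participant misses the visit entirely". In that case "that period will not contribute to the compliance or exposure calculation unless the bottles are returned at a later visit". The date-based measures are outside it.

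On supply, Protocol 9.1 issues two bottles of 40 tablets at Visits 2, 4 and 5; "this will provide the patient with 80 tablets to cover the 4 weeks of dosing between visits", with some spare. Patients are told to empty one bottle before starting the other, and to bring both back.

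The SAP does not write out how tablets taken is derived. Later in 11.2 it equates failing to return more than 8 tablets in a 4-week interval with compliance above 114%.

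**The concern.** The same exclusion does different things to a ratio and to a sum. In compliance, an unaccounted period leaves the numerator and denominator together, and the result describes the periods that were counted. Exposure days has no denominator. Leaving a period out of a running total gives the same number as recording that no tablets were taken, so unknown dosing is reported as no dosing.

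The exception for bottles returned later works for the first two periods. For the Week 8 to Week 12 period, Visit 6 is the last scheduled treatment visit, so only an unscheduled return could rescue it.

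The trigger is also all-or-nothing. Once anything comes back, the 114% equivalence implies that whatever is missing counts as swallowed. A participant who leaves an unfinished bottle at home is then over-credited, while one who leaves both at home is under-credited.

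At stake is whether a descriptive dose-received summary in a fixed-dose trial means what its label says, and whether it can be reconciled with the two measures reported beside it.

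**Working it through.** **Inputs**

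- 2 tablets per night (Protocol 9.2).
- 40 tablets per bottle, two bottles per dispensing, three dispensings (Protocol 9.1): 80 tablets per period.
- Three nominal 28-night periods, 84 nights in all (Protocol 10.4 and 10.5): 2 × 28 = 56 tablets needed per period, so 80 − 56 = 24 spare.
- Exposure days = tablets taken ÷ 2, rounded up; compliance = taken ÷ assigned × 100 (SAP 11.2).
- Assumption: tablets taken = dispensed − returned, whenever anything is returned.

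**Reproducing the SAP's own figure.** Eight unreturned tablets counted as taken give (56 + 8) ÷ 56 = 114.3%. This matches the 114% in SAP 11.2 and supports the assumption.

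**A participant who doses on all 84 nights.** The first two periods are fully accounted for (112 tablets). Only what comes back at Week 12 varies.

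| Returned at Week 12 | Tablets counted, last period | Exposure days | Compliance, last period | Compliance, overall | Days by dates |
|---|---|---|---|---|---|
| Both bottles (24 tablets left) | 80 − 24 = 56 | 168 ÷ 2 = 84 | 100% | 168/168 = 100% | 84 |
| Nothing | excluded | 112 ÷ 2 = 56 | excluded | 112/112 = 100% | 84 |
| Empty first bottle only | 80 − 0 = 80 | 192 ÷ 2 = 96 | 80/56 = 142.9% | 192/168 = 114.3% | 84 |
| Second bottle only (24 left) | 80 − 24 = 56 | 168 ÷ 2 = 84 | 100% | 168/168 = 100% | 84 |

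The same 28 nights of dosing are therefore credited as 28, 0, 40 or 28 days. The no-return case loses 28 of 84 days (33.3%). The empty-bottle case gains 12 days on 28 (43%). Forgetting the empty bottle does no harm; forgetting the part-used one does.

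**Visit windows.** Visit 5 may fall on Day 51 to 61 and Visit 6 on Day 79 to 91. The days lost by a non-returner at Week 12 then run from 79 − 61 = 18 to 91 − 51 = 40.

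**Effect on an arm mean.** The documents give no non-return rate, so this is by assumption. If a proportion *f* of full completers return nothing for one period, the mean falls by 28 × *f*:

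- 5%: 1.4 days (84 to 82.6)
- 10%: 2.8 days (84 to 81.2)
- 20%: 5.6 days (84 to 78.4)

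**The case against.** **Exposure is measured mainly by dates.** This stands. Exposure days is introduced as an addition, the unreturned-bottle convention does not reach the date-based measures, and the forgetful completer still shows about 84 days there. A reader might infer that the trial will misreport how long participants were treated; the documents do not support that.

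**Other tablet-based information exists.** This also stands. Compliance uses the same counts and is summarised by arm, and tablet counts and reasons for discrepancies are listed. Exposure days is not the only tablet-based measure, and compliance under the no-return rule behaves sensibly.

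**Partial returns are already caught.** Largely true. SAP 11.2 summarises results above 114%, and Protocol 9.5 requires an investigator evaluation and a deviation when more than 8 tablets are unaccounted for. The 142.9% case would trigger all of this. None of it changes the exposure-days value that enters the summary.

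**Giving no credit for unverified doses is conservative.** Only in one direction. The implied handling of a partial return credits doses just as unverified. A sum also cannot withhold credit without asserting a value, and the value asserted is zero.

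**Lost to follow-up.** A reader might infer that exposure days is biased low for everyone lost in their final period. The documents do not support this. SAP 11.2 gives such participants a last dose date on the day before their last attended visit, so the date-based measure also gives no credit afterwards. What they actually took is unknown.

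**Differences between arms.** A reader might also infer a distorted comparison between arms. That would need return behaviour to differ by arm, and the documents say nothing on that.

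**Conclusion.** The point holds as a minor defect in one supplementary descriptive measure. As written, the rule gives a fully dosed completer who returns nothing at Week 12 an exposure-days value of 56, against about 84 days by dates and 100% compliance in the same section. That result follows directly from the stated rule.

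The opposite error, 40 days credited for a 28-night period, rests on tablets taken meaning dispensed minus returned. The SAP implies this through the 114% figure but does not state it. It also requires that the part-used second bottle is the one left behind.

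The group effect is 28 days times the proportion of completers affected, and that proportion is an assumption. Exposure days feeds no efficacy test, model or population definition, so efficacy conclusions are untouched.

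**What to change.** Amend SAP 11.2 as follows.

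1. Define tablets taken as dispensed minus returned.
2. Keep the present exclusion for compliance, including the allowance for bottles returned later.
3. Set exposure days to missing for any participant with a period in which no bottles, or only one of the two, came back. Report by arm the number of participants and the number of periods affected.
4. As a supportive summary, for participants who attended the visit closing that period, fill it with the calendar nights from dispensing to that visit multiplied by their compliance in the counted periods. Do not apply the fill to participants lost to follow-up: they have no closing visit and their assigned last dose date precedes the gap, so the fill would be zero or undefined. Leave them missing.

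For the worked example the fill gives 28 × 100% = 28 days, so 56 + 28 = 84, in both the no-return and the empty-bottle case.

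The cost is a few SAP sentences and minor programming, with no change to trial conduct. The downside is that some participants leave the main exposure-days summary even though their other periods were validly counted, including some whose only missing bottle was empty. The supportive fill is an estimate, and should be labelled as one.

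### The >114% compliance limit in SAP 11.2 does not reproduce the more-than-8-tablet rule it stands for, so a few accountability cases are classified differently by the two rules

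*SAP*

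**What the plan says.** Two kinds of rule cover missing or over-used tablets.

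**Tablet count.** Protocol 9.5 requires a written investigator evaluation, entered on the CRF, in this case: "If more than 8 tablets cannot be accounted for at any of the visits where drug is returned (week 4, 8 or 12". It adds that situations "when more than 8 tablets cannot be accounted for, should be recorded as deviations". SAP 11.2 first follows the same line and names as a deviation "All pill count shortage (negative pill count) of greater than 4 doses (8 tablets) per 4-week assessment period", next to between-visit compliance below 70%.

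**Percentage.** Later in SAP 11.2 comes the sentence "Compliance between 70% to 114% will not be considered a protocol deviation". The over-use summary is then defined by over-use or missing tablets "resulting in >114% compliance for any visit (e.g., failure to return >8 tablets per 4 week interval". The listings that go with this summary show the participant's reason and the investigator's view on abuse, misuse or diversion.

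Compliance in SAP 11.2 is tablets taken divided by tablets assigned, times 100. The SAP does not say how tablets assigned are counted when an interval is not 28 nights.

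**The concern.** The SAP treats above 114% and more than 8 tablets as the same threshold. A percentage depends on the length of the interval and a count does not, so they can coincide at only one interval length. The visit windows allow the interval to vary widely.

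Two outputs depend on this: whether a shortage counts as a deviation, and who appears in the over-use summary. A participant above the protocol's count may have an investigator evaluation on the CRF that the over-use listing does not show. A participant at or below the count may be listed although the protocol asked for no evaluation.

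**Working it through.** **Inputs**
- Dose: "Patients will be reminded that only 2 (two) tablets are allowed per day" (Protocol 9.2), so 2n tablets are expected over n nights. Reading tablets assigned in this way is an assumption.
- Supply: "this will provide the patient with 80 tablets to cover the 4 weeks of dosing between visits" (Protocol 9.1).
- Visit windows (Protocol 10.4 and 10.5): Day 28 ± 5, Day 56 ± 5, Day 84 −5/+7.
- Unaccounted-for tablets, u: dispensed, minus returned, minus 2n. The percentage treats them as taken.

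**The plan's own figure.** At 28 nights, 2n = 56. With u = 8, compliance is 64/56 = 114.29%, or 114% in whole percent. So 114% is evidently 8/56 rounded down.

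**Possible intervals.** Visit 2 to 4: 23 to 33 nights. Visit 4 to 5: 51 − 33 = 18 to 61 − 23 = 38. Visit 5 to 6: 79 − 61 = 18 to 91 − 51 = 40. Overall: 18 to 40 nights.

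**Formula.** Compliance = 100 × (2n + u)/(2n). It exceeds 114% when u > 0.28n. The exact percentage for 8 tablets is 100 × (1 + 8/(2n)): 117.4% at 23 nights, 114.29% at 28 and 112.1% at 33.

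**Comparison** of above 114% (unrounded) with u > 8, total use capped at 80 tablets:

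| Nights | Cases where the rules differ | Example | Met by |
|---|---|---|---|
| 18–21 | u = 6, 7, 8 | 18 nights, 6: 42/36 = 116.7% | percentage only |
| 22–24 | u = 7, 8 | 23 nights, 7: 53/46 = 115.2% | percentage only |
| 25–28 | u = 8 | 28 nights, 8: 64/56 = 114.29% | percentage only |
| 29–32 | none | | |
| 33 | u = 9 | 75/66 = 113.6% | count only |
| 34 | u = 9 | 77/68 = 113.2% | count only |
| 35 | u = 9 | 79/70 = 112.9% | count only |
| 36–40 | none: at most 80 − 72 = 8 spare tablets | | |

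That is 12 + 6 + 4 = 22 percentage-only cases and 3 count-only cases, 25 in all. The last row holds only without the replacement drug that Protocol 9.3 allows.

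**Rounding.** The SAP's reporting convention (Appendix 1, 14.1.2) is one decimal, so the 28-night case is 114.3% and still above 114. Rounding to whole percent removes it, and also the case of 6 tablets at 21 nights (48/42 = 114.29%). It leaves the three 9-tablet cases. It also creates two new misses, 9 tablets at 32 nights (73/64 = 114.06%) and 10 at 35 nights (80/70 = 114.29%), because both round to 114%.

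**Other denominators.** If expected use is fixed at 56 for both rules, only the case of exactly 8 tablets remains. If the denominator is the 80 tablets dispensed, compliance above 114% cannot occur without replacement drug.

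**The case against.** **A rate, not a count.** The SAP's count rule and its explanation of 114% both refer to a 4-week period. Read as a rate, 9 tablets over 33, 34 or 35 nights is 9 × 28/33 = 7.6, 7.4 or 7.2 per 28 nights, and the two SAP rules then agree. On that reading they differ only at the edge of the limit (6 tablets at 21 nights, 8 at 28, 9 at 32, 10 at 35), and not at all with whole-percent rounding. This is a fair reading of the SAP. It does not cover Protocol 9.5, which counts tablets at each return visit with no reference to a period. The conflict between protocol and SAP at 33 to 35 nights therefore stands.

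**The percentage sentence may address only the percentage criterion.** On this view the tablet count remains a separate ground for a deviation. That is possible, but the sentence carries no such limit.

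**Nothing is lost.** Protocol 9.5 triggers the evaluation and the deviation by count, whatever the SAP percentage is. SAP 11.2 lists tablet counts, compliance by visit and reasons for every discrepancy. SAP 8.2 settles deviations at a blinded data review meeting before lock. All of this stands, and it limits the harm.

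**A stronger reading.** A reader might infer that all 25 differing cases are conflicts about deviations, or that the deviation table depends on which sentence is programmed. The documents do not support either. No sentence makes compliance above 114% a deviation; SAP 11.2 says only what is not one. The 22 cases with 8 or fewer tablets affect entry to a descriptive summary and nothing more, and the review meeting decides the deviations.

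**Conclusion.** The point holds in a narrow form. The 114% limit does not deliver the rule it is explained as.

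- **Explicit conflict about deviations:** exactly 9 unaccounted-for tablets over 33, 34 or 35 nights. Protocol 9.5 makes this a deviation, the 70% to 114% sentence in SAP 11.2 says it is not, and the over-use summary omits it. This rests on tablets assigned being 2 per night of the interval.
- **Mismatch at the nominal interval:** exactly 8 tablets over 28 nights enters the summary without being more than 8. This holds whether the denominator is 2 per night or a fixed 56, and with either it disappears only if compliance is rounded to whole percent.
- **Short intervals:** 6 to 8 tablets can enter the summary. This affects selection for the summary only.

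Severity is minor. The effect is confined to deviation reporting and the abuse/misuse summary. No analysis population in SAP section 6 is defined by compliance, and the efficacy analyses are untouched. The documents do not give the number of participants affected; it is likely to be small.

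**What to change.** In SAP 11.2:

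1. Reword the 70% to 114% sentence so that a visit is free of a compliance deviation when compliance is at least 70% and no more than 8 tablets are unaccounted for at that visit.
2. Select the over-use and unaccounted-for summary by the same count, more than 8 tablets at the visit, as in Protocol 9.5 and the SAP's own shortage rule.
3. State the compliance denominator, for example 2 tablets times the nights in the interval.
4. Keep percent compliance for the descriptive categories.

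The cost is SAP wording only, since the tablet counts are already collected. There is one downside: a count ignores interval length. Up to 8 extra tablets in a short interval (8 over 18 nights is 44/36 = 122.2%) would leave the over-use summary and show only in the by-visit compliance listing and the category above 100%.
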